**SUMMARY**

Object of the investigation	Embozene TANDEM™ 100 µm microspheres
Full Title	Multicenter spanish observational, prospective study to evaluate the safety of transarterial Chemoembolisation (TACE) with tight calibrated and doxorubicin-releasing microspheres of 100 microns in the treatment of Hepatocellular Carcinoma (HCC)
Study Identifier	FJD-TAN-2014-01. Version 1.1, March 15 th , 2015
Study Description	Prospective Post-authorization study of follow-up (EPA-SP)
Promotor	[name], MD, PhD Vascular and Interventional Radiology Service Ramon y Cajal University Hospital. [name]. [contact] [contact]
Principal Investigator	[name], MD, PhD Vascular and Interventional Radiology Service Ramon y Cajal University Hospital. [name]. [contact] [contact]
Primary Objective	Safety and tolerability of DEB-TACE of non-resectable HCC, using 100-µm doxorubicin-loaded microspheres
Secondary Objectives	6-, 12- and 24-month local tumor response and 2-year Over All Survival
Number of Investigators	10 Spanish University Hospitals (See annexed II)
Number of participants	130
Inclusion Criteria	Confirmed diagnosis of HCC, Subject is competent and willing to provide written informed consent, Adults (male or female) patients ≥ 18 years of age, ECOG performance status is 0 – 1 or Child-Pugh classification is A, B7, Multinodular or single nodular tumor ≥3 – 9 cm, No invasion in the major blood vessels, Proper blood, liver, renal, heart function: testing result within 2 weeks of start, No current infections requiring antibiotic therapy, Not actively on anticoagulation drugs, Measureable disease per the modified Response Evaluation Criteria in Solid Tumors (mRECIST), Life expectancy ≥ 6 months
Exclusion Criteria	(ECOG performance status ≥2; or Child-Pugh class B8 or C, Bilirubin levels >3 mg/dl, HCC with large vessel or biliary duct invasion, diffuse HCC or extrahepatic spread, Patients in which any of the following are contraindicated or present (The use of doxorubicin, MRI or CT scans, Hepatic embolization procedures, WBC < 3000 cells/mm  , neutrophil < 1500 cells/mm  , Cardiac ejection fraction < 50 percent, Elevated creatinine greater than or equal to 2.5 mg/dl, Impaired

	clotting test, AST and/or ALT >5x ULN or, when greater >250 U/L, Known hepatofugal blood flow, Arterio-venous shunt, Arterio-portal shunt, Main stem portal vein occlusion), Women who are pregnant or breast feeding, Allergy to iodinated contrast used for angiography, Tumor burden of more than 50% of liver, Patients with objective signs of active bacterial, viral (HIV), or fungal infection, Other primary malignancies or evidence of metastatic disease)
Enrollment Period	1 year from approval date
Clinical Visits	1 pre-treatment, 6 post-treatment (1, 3, 6, 12, 18 and 24 months)
Statistical Analysis	NA
Subject Follow-up	2 year post final treatment
Study Calendar	The study is expected to start in March 2015. The recruitment period will last 1 year, and the follow-up period 2 years, so the total duration of the study is estimated at 3 years, ending in 2018

## BACKGROUND AND JUSTIFICATION OF THE STUDY

According to the guidelines of the European Association for the Study of the Liver (EASL) and the American Association for the Study of Liver Diseases (AASLD), radiofrequency, surgery and liver transplantation are considered radical curative treatment modalities for HCC in early stage as long as they are anatomically / clinically feasible (1,3-5).

Transarterial chemoembolization (TACE) is the formal indication for the treatment of intermediate stage HCC. This treatment has a level of evidence 1 A increasing the overall survival of these patients. TACE is performed using ultraselective catheterization techniques, under high quality fluoroscopic guidance, using microcatheters. The intrahepatic artery or arteries that nourish the HCC are channeled as selectively as possible to release the therapeutic agent there (6-8).

There are considerable variations in the embolization-chemoembolization technique in relation to the choice of materials, aspects of the procedure, drug and dose used, "end point", number of sessions and space between them etc etc ... (9). There are basically two ways to apply the TACE. Conventional TACE (c-TACE), initially described in 1983, is in which lipiodol is emulsified with doxorubicin and acts as a cytostatic vehicle (10). In the past decade, synthetic microspheres have been developed that can be preloaded with doxorubicin or irinotecan drug eluting beads giving rise to TACE with microspheres (deb-TACE). This has the advantage of increasing the dose and exposure time between the neoplastic cells and the tumor while practically nullifying the systemic effect of doxorubicin. The appearance of the synthetic microspheres that are both vehicle and drug-releasing has decreased the toxicity of the treatment and has also decreased its variability (11). However, there are still many unknowns regarding the ideal TACE.

The current trend in most Western countries is to treat HCC by deb-TACE versus c-TACE. Deb-TACE has proven to be very effective in terms of local disease control, with a tendency also towards better overall survival rates although this last point has not yet been confirmed (11-15). Regarding the ideal size of the microsphere that should be used in the hepatocarcinoma deb-TACE, there is still no consensus. This is so to the point that in the current clinical guidelines in force there is no specific recommendation in this regard (1,16-18). In the initial safety and pharmacokinetic studies conducted 10 years ago when this technique was born, microspheres between 500 and 700 microns were used (19). However, today in normal clinical practice it is considered that smaller spheres have more intratumoral penetrance. There are groups that use spheres of 300 to 500 microns (13), others that prefer those of 100 to 300 microns (14) and groups that advocate the use of spheres smaller than 100 microns (20). Experimental studies in animals have shown that reducing the size of the microspheres increases their penetration into the tumor, increasing the amount of drug released in the target tissue, thus achieving a more intense tumoricidal effect (21,22). However, ischemia and lesion of hepatic bile radicals is a potential side effect that arises if very small particles are used. A recent Italian multicenter study shows that in QETA with microspheres smaller than 100 microns (M1 DC Beads, BTG, UK) the safety and efficacy of treatment is similar or somewhat better than that published for other microsphere sizes (23). On the other hand, the recommendations and standard of treatment for QETA in liver metastases from colorectal carcinoma clearly advise the use of microspheres from 75 to 100 microns (24).

Three different brands of drug-releasing microspheres are currently approved for use in the European market. DC Beads® (BTG, Farnham, Surrey, UK), HepaspHERE® (Merit Medical) and Tandem® (Celonova). Most of the literature published on “drug eluting beads” has been made using the DC Beads® platform, which currently has the largest market share. The Tandem® microspheres are of more recent commercialization (May 2012) and because of their characteristics they have a number of potential advantages although at the moment clinical studies on this product are not as abundant as on DC Beads.

In the Jiménez Díaz University Hospital, the TACE was introduced for the treatment of hepatocarcinoma in 1994. In July 2006, the first case of TACE was carried out using microspheres preloaded with doxorubicin. The experience is extensive with more than 250 treatment sessions carried out so far. In 2011 we were pioneers in Madrid in the use of the particle M1-DC Bead from 70 to 100  $\mu$ . Our usual clinical practice at this time is to use small spheres for hepatocellular carcinoma, reserving 300 or 500 micron particles only for those very bulky tumors with suspicion or evidence of arteriovenous fistulas. In March 2013, the FJD began with the use of 100 $\mu$  Tandem microspheres, with 18 treatments with good results in terms of local tumor control. At the meeting on embolization that the Spanish Society of Vascular and Interventional Radiology held in Madrid last February, a consensus was reached that the 100 micron microsphere was safe and therefore its use was recommended as usual practice for the TACE of the CHC (25). In European hospitals the trend is similar using microspheres of 70 to 150 $\mu$  (DC Bead M1) or microspheres calibrated of 100 or 75 $\mu$  (Tandem) without so far a higher complication rate has been reported. Annex I lists the Spanish and European centers that currently use 100 or 75 $\mu$  Tandem particles for the treatment using TACE of the HCC.

The TANDEM® 100 $\mu$  microsphere has shown in experimental works a pharmacokinetics similar to those of DC Bead. It has a very accurate calibration compared to other microspheres in the market. It has a high loading capacity for doxorubicin and does not change its size or consistency once the drug is inside. The inflammatory reaction it causes is low thanks to the hydrogel that covers it. It is designed to penetrate deeply and homogeneously in intratumoral vascularization (26-30).

The purpose of this study is to describe the safety and tolerability of the use of Embozene TANDEM™ microspheres in patients with unresectable HCC in whom administration of TACE is indicated.

### 1.1 Embozene TANDEM™ Microspheres

Embozene TANDEM™ microspheres are non-absorbable, biocompatible, spherical hydrogel microparticles with a precise calibration that are coated with an inorganic perfluorinated polymer (Polyzene®-F). The microsphere design features allow Embozene TANDEM™ microparticles to be loaded with drugs (such as doxorubicin hydrochloride and irinotecan) to deliver a constant, controlled and local dose to the embolized tumor (30).

Embozene TANDEM™ microspheres are CE marked (CE0297) (May 2012) and are indicated for embolization under the following conditions:

- **Hepatocellular Carcinoma**
- Arteriovenous malformations
- Uterine leiomyomas
- Hypervascular tumors
- Tumors of the head, neck, torso and skeletal system
- Hemorrhages and trauma
- Presurgical tumor embolization except in the Central Nervous System

Usually **3 ml syringes with 100 µm Embozene TANDEM™ microspheres are used** (device reference number: 10730-TS0). Embozene TANDEM™ microspheres are presented in syringes, suspended in a sterile and non-pyrogenic physiological saline solution. Embozene TANDEM™ microsphere syringes are packed in a sterile tray sealed with a plastic film. The color-coded label indicates the size of the microsphere contained in the syringe.

## 1.2 Route of activation and mechanism of action

Embozene TANDEM™ microspheres have been designed to ionically absorb and bind positively charged molecules. The antineoplastic agent doxorubicin hydrochloride is an effective positive loading drug for the treatment of HCC. This drug, when administered systemically (intravenously), has an important toxic profile that normally limits its use. After their local and selective administration in the tumor through an intra-arterial microcatheter, the microspheres release the drug (doxorubicin) in the embolic zone by diffusion. The release of the drug depends on its physical properties, the concentration of local ions and the local pH. The released doxorubicin is then dispersed through the surrounding tissue and interacts with the metabolizing cells to inhibit duplication and ultimately kill the affected cells.

## 1.3 Dosage and administration

The dose of doxorubicin is the standard for TACE with 50 mg of doxorubicin per ml of microspheres. Embozene TANDEM™ microspheres can be loaded with 98 ± 2% doxorubicin hydrochloride (in two hours, although one hour is sufficient) at room temperature. TANDEM™ capsules loaded with doxorubicin (TANDEM™ -DOX) remain stable for 48 hours at 4 ° C in the dark. TANDEM™ -DOX microspheres are mixed with a contrast agent and slowly injected through an intra-arterial microcatheter into the vasculature of the tumor until stasis is achieved. The maximum dose per treatment session is 150 mg of doxorubicin in 3 ml of 100 µm TANDEM™ doxorubicin

## 1 OBJECTIVES OF THE STUDY

### 1.1 Primary Objective

The primary objective is to evaluate the **tolerance and safety** of TACE with TANDEM™ 100 $\mu$  microspheres preloaded with doxorubicin, describing:

- Appearance and intensity of post-embolization syndrome in the 1st week after treatment
- Major adverse events during the 30 days after TACE.
- Minor adverse events during the 30 days after TACE.
- Mortality derived from treatment.

### 1.2 Secondary Objectives

- **Local tumor control** based on the pattern of devascularization according to RECIST 1.1 criteria (2). If a patient is referred to a liver transplant: local tumor control based on histological analysis
- **2 year overall survival (OS)**

## 2 STUDY DESIGN

The study has been conceived as a multicenter, international, observational, post-authorization, prospective follow-up study (EPA-SP). It is planned to include between 100 and 150 patients with non-removable HCC treated with the 100  $\mu$ m Embozene TANDEM™ microspheres (drug-releasing microparticles with doxorubicin loading) for enhanced cytotoxic transarterial embolization therapy with hepatocellular carcinoma microparticles.

10 University Hospitals of Spain with recognized experience in treatments with TACE will participate. Each center must recruit a minimum of 5 patients.

All the associated researchers are certified in Vascular and Interventional Radiology with recognized experience in liver cancer intervention, in the administration of small embolic microspheres, in the management of microcatheters and in ultraselective catheterization.

## 3 STUDY POPULATION

### 3.1 Target population

Patients with confirmed HCC and stage B according to the BCLC classification. Patients with a less advanced stage (BCLC stages 0 and A) but who are not candidates or expressly reject radical treatments with surgery or radiofrequency.

Three possible groups of patients are considered:

- A.- Patients unfit for surgery or liver transplantation due to tumor extension, age and / or comorbidities.
- B.- Patients not eligible for a liver transplant for exceeding the Milan criteria but with the possibility of experiencing a backward step to a previous stage (down stage) by TACE within these criteria
- C.- Patients eligible for a liver transplant on the waiting list: to prevent tumor progression while on the waiting list.

### 3.2 Inclusion Criteria

1. Confirmed diagnosis of CHC according to EASL criteria and staged according to BCLC criteria
2. Patients with indication for TACE with 100 micron microspheres according to the usual practice of the center
3. Subjects in full power and willing to give their written informed consent to participate in the study.
4. Adult patients (men or women)  $\geq$  18 years of age.
5. Good quality of life. ECOG 0-1.
6. Child-Pugh preserved liver function  $\leq$  B7.
7. Absence of tumor invasion in the main Porta vein or main bile ducts
8. Possibility of undergoing diagnostic tests with CT or MRI.
9. Liver, cardiac and renal function, preserved, with these test results in two weeks from the registration of this study:
  - a. White blood cells count:  $> 2000 / \text{mm}^2$
  - b. Absolute neutrophil count:  $> 1000 / \text{mm}^3$
  - c. Quick Index  $> 50\%$
  - d. Platelets count  $> 5 \times 10^4 / \text{mm}^3$  and.
  - e. Serum bilirubin  $< 3.0 \text{ mg / dL}$
  - f. ASL, ALT 5 times within the normal range
  - g. Serum creatinine  $< 2 \text{ mg / dL}$
  - h. Hemoglobin  $> 9.0 \text{ g / dL}$
  - i. Non-unstable coronary disease or recent MI ( $< 4$  weeks)
10. Absence of concomitant infections that require antibiotic treatment.
11. Disease measurable by the modified criteria for evaluating the response in solid tumors (mRECIST 1.1).
12. Life expectancy greater than six months.

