### 3.3 Exclusion Criteria

1. Symptomatic patient ECOG  $\geq 1$
2. Poor liver function, Child-Pugh  $\geq B8$ .
3. Ascites or encephalopathy
4. Extrahepatic tumor disease
5. Tumor invasion of the main portal vein
6. Serum bilirubin  $> 3 \text{ mg / dL}$
7. Cre clearance  $\leq 60 \text{ mL / min}$
8. Patients in whom the following elements are contraindicated or present:
  - a. Doxorubicin use

- b. Documented allergy to iodinated contrast
- c. CT and MRI scans
- d. Liver embolization procedures
- e. White blood cell count <2000 cells / mm^3
- f. Neutrophils count <1500 cells / mm^3
- g. Cardiac ejection fraction < 50 percent
- h. Platelet count <5 x 10^4 / mm^3, PT-INR > 2.0)
- i. AST and / or ALT > 5x or when they exceed > 250 u / l
- j. Known Hepatofugal blood flow
- k. Gross intrahepatic A-V fistula

- 9. Pregnant or lactating women.
- 10. Tumor load greater than 50% of liver volume.
- 11. Active fungal or bacterial infection.
- 12. Other concomitant tumors.
- 13. Any comorbidity, condition or event that, in the opinion of the investigator, puts the patient at an undue risk that discards the use of DEB-TACE.
- 14. Patients who do not wish to participate and / or who refuse to give their written consent

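### Eligibility rules conflict: ECOG 1 is both included and excluded, and the Summary and section 3 differ on white cells, creatinine and tumour size, so centres could enrol different populations

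*Combined protocol and SAP*

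**What the plan says.** Eligibility is set out in three places: the Summary, section 3.2 (inclusion) and section 3.3 (exclusion).

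- **ECOG.** Section 3.2 item 5 reads "Good quality of life. ECOG 0-1". Section 3.3 item 1 excludes symptomatic patients, with the threshold printed as ECOG 1 or above. The Summary includes ECOG 0–1, and its exclusion reads "ECOG performance status ≥2; or Child-Pugh class B8 or C".
- **White cells.** The Summary excludes "WBC < 3000 cells/mm"³. Section 3.3 excludes "White blood cell count <2000 cells" per mm³, and section 3.2 item 9a requires more than 2000.
- **Renal function.** Section 3.2 item 9g requires serum creatinine below 2 mg/dL. The Summary's only numeric renal limit is the exclusion "Elevated creatinine greater than or equal to 2.5 mg/dl", alongside the unquantified inclusion "Proper blood, liver, renal, heart function: testing result within 2 weeks of start". Section 3.3 item 7 also excludes creatinine clearance of 60 mL/min or less.
- **Tumour size.** The Summary requires a tumour of 3–9 cm. Sections 3.1 to 3.3 give no diameter limit. The exclusion for tumour load above 50% of the liver appears in both the Summary and section 3.3.
- **Neutrophils.** Section 3.2 item 9b requires more than 1000/mm³. Section 3.3 and the Summary both exclude counts below 1500.

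Nothing in the document says which list prevails.

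**The concern.** The study has no comparator. Its results are rates in the patients enrolled: post-embolization syndrome, adverse events and deaths to 30 days, tumour response, and 2-year survival. Eligibility fixes both the denominator of those rates and the population they describe.

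Ten hospitals recruit. A centre working from the Summary, one working from section 3.2 and one applying section 3.3 literally would accept different patients, and each could say it followed the protocol. The limits in conflict also bear on the outcomes. Renal failure, defined as a doubling of creatinine, is a listed early adverse event in section 5.1. Tumour size bears on local response.

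Section 9.2 asks for eligibility deviations to be documented and telephoned to the monitor. That helps, but a deviation cannot be identified while the rule contradicts itself. Section 5.1 does not list ECOG among the patient and disease variables, so a mixture on that criterion might not show in the results.

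**Working it through.** **Step 1. Compare the lists.**

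| Criterion | Summary | Section 3.2 | Section 3.3 | Patients treated differently |
|---|---|---|---|---|
| ECOG | include 0–1; exclude ≥2 | include 0–1 | exclude ≥1 | ECOG 1: in under the Summary and 3.2, out under 3.3 |
| White cells (/mm³) | exclude <3000 | require >2000 | exclude <2000 | above 2000 and below 3000: out under the Summary, allowed by section 3 |
| Creatinine (mg/dL) | exclude ≥2.5 | require <2 | none | 2.0 to below 2.5: not barred by the Summary's number, out under 3.2 |
| Creatinine clearance (mL/min) | none | none | exclude ≤60 | clearance ≤60 with creatinine <2: meets both creatinine limits, out under 3.3 |
| Tumour diameter | 3–9 cm | none | none | <3 cm or >9 cm with load ≤50%: out under the Summary, not barred by section 3 |
| Neutrophils (/mm³) | exclude <1500 | require >1000 | exclude <1500 | none if the exclusion governs; the two exclusions agree |

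The ECOG conflict lies inside section 3, so preferring the body to the Summary does not resolve it. The white-cell, creatinine and diameter rows are differences between the Summary and section 3. The clearance row is a rule found in one list only. The neutrophil row is a wording point.

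**Step 2. Reproduce the plan's own figure.** Sections 3.4 and 6.2 give n = 130, an assumed event proportion of 1.00%, a two-sided asymptotic 95% interval and a precision of 1.71%.

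- Half-width = 1.96 × √(0.01 × 0.99 / 130) = 1.71%. This matches.

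**Step 3. Put the conflict on that scale.**

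- Expected events at the assumed rate: 130 × 0.01 = 1.3.
- One patient with an event: 1/130 = 0.77 percentage points.
- Relative to the planned half-width: 0.77 / 1.71 = 0.45.
- Each 10% of enrolled patients with ECOG 1: 0.10 × 130 = 13 patients who breach 3.3 item 1. If every centre applied 3.3 literally, the number would be zero.

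**Step 4. Dependence on n.** Section 2 plans 100 to 150 patients, and 10 patients at each of 10 centres gives 100.

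- n = 100: 1/100 = 1.00 point; half-width 1.95; ratio 1.00/1.95 = 0.51.
- n = 150: 1/150 = 0.67 point; half-width 1.59; ratio 0.67/1.59 = 0.42.

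**What cannot be computed.** The documents give no distribution of ECOG, white cells, renal function or tumour size, so the number of patients in each group of Step 1 is unknown.

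**The case against.** The strongest reply is that two ordinary conventions remove the ambiguity: the body of a protocol overrides its summary, and an exclusion overrides an inclusion. Together they give one answer for every row of the table. Neither is written down, however. Applying them would leave the ECOG 1 entry in 3.2 without effect and the Summary's ECOG lists wrong, so a correction would still be needed.

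On ECOG, three of four statements agree (both Summary entries and 3.2). Only 3.3 item 1 departs, and it carries the qualifier that the patient is symptomatic. A slip is plausible. Even so, the printed threshold is 1 or above, and 3.2 accepts ECOG 1 without qualification.

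Several other items are weaker than the ECOG conflict, and that part of the objection stands. The clearance limit can be applied together with the creatinine limit. For tumour size, section 3 has no diameter limit rather than a different one. The white-cell and creatinine differences matter only if a centre enrols from the Summary, which is possible but not shown.

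Some variation between centres is also built in: 3.2 item 2 relies on each centre's usual practice, and 3.3 item 13 on investigator judgement. That variation is intended and stated. Variation from contradictory limits is neither.

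Finally, 0.77 points is the weight of any single event among 130 patients, and the 10% share is illustrative. Both give a scale and do not measure the effect of the conflict. The 1.00% rate is for an unspecified event, and the plan gives no rate for post-embolization syndrome or minor events.

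**Conclusion.** The concern holds. Read literally, section 3 makes an ECOG 1 patient both eligible and ineligible, and the Summary defines a different population from section 3 on white cells, creatinine and tumour diameter. This is an error in the text as written and should be corrected.

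The numerical effect is unknown. The figures of 13 patients per 10% and 0.77 points per event (about 45% of the planned ±1.71) rest on n = 130, the assumed 1.00% event rate and, for the first, a share chosen for illustration. That centres would in fact apply different lists is an inference from ten recruiting centres and no stated precedence. No view is taken here on which limit is right.

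**What to change.** Amend the protocol so that the Summary, 3.2 and 3.3 give one limit each for ECOG, white cells, neutrophils, renal function and tumour size, and no patient meets both an inclusion and an exclusion. The choice of limits belongs to the sponsor and investigators. A line-by-line comparison should also cover rules that appear on one side only: anticoagulation and HIV (Summary), ascites or encephalopathy (3.3), and the Summary's joining of ECOG and Child-Pugh by an or.

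If patients are already enrolled, list those who fall between the conflicting limits and show the primary safety rates with and without them. For an event as rare as 1% this comparison will show little. It will be more informative for commoner outcomes.

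The cost is one wording amendment, with IRB approval before implementation (sections 9.3 and 8.1). No extra tests are needed. A stricter choice on any criterion could slow recruitment within the one-year enrolment period.
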